7 DRUG FORMULATION AND ADMINISTRATION

7.1 Poly-ICLC (Hiltonol ®)

7.1.1 Description

CONFIDENTIAL

This document is confidential. Do not disclose or use except as authorized.

Poly-ICLC is a synthetic, nuclease resistant, hydrophilic complex of polyinosinic and polycytidylic acid, stabilized with poly-L-lysine and carboxymethylcellulose.

[figure not shown]
[figure not shown]
[figure not shown]

Figure 1: Structure of poly-ICLC

CONFIDENTIAL

This document is confidential. Do not disclose or use except as authorized.

7.1.2 Form

Poly-ICLC is supplied by Oncovir in single-dose vials containing 1 mL of 2 mg/mL opalescent white suspension. Each mL of poly-ICLC for injection contains 2 mg of poly-IC, 1.5 mg poly-L-lysine, and 5 mg sodium carboxymethylcellulose in 0.9% sodium chloride solution, adjusted to pH 7.6-7.8 with sodium hydroxide.

7.1.3 Storage and Stability

Poly-ICLC is stable at room temperature for brief periods (days). For long term storage, it should be refrigerated at ca. 40°F (2-8°C). Poly-ICLC should NOT be frozen.

7.1.4 Compatibility

Poly-ICLC will be mixed with personalized neoantigen peptides just prior to use to prepare the final product (NeoVax).

7.1.5 Handling

There are no specific handling instructions for poly-ICLC.

7.1.6 Availability

Poly-ICLC is an investigational agent and has been purchased from Oncovir, Inc. Vials of poly-ICLC sufficient for this clinical trial have been shipped from the Hiltonol® storage facility (Bellwyck Packaging, Mississauga, Ontario, Canada) to the DFCI Pharmacy and are currently stored under conditions appropriate for this investigational agent.

7.1.7 Preparation

CONFIDENTIAL

This document is confidential. Do not disclose or use except as authorized.

Poly-ICLC is supplied as an opalescent white suspension. It will be directly withdrawn from the vial under sterile conditions and mixed with the personalized neoantigen peptides (see section 5.2.1.3).

7.1.8 Administration

Following mixing with personalized neoantigen peptides, the vaccine (peptide + poly-ICLC) will be administered as follows: using one syringe/needle per site 0.5 mL will be administered intradermally and 0.5 mL will be administered subcutaneously.

7.1.9 Ordering

Poly-ICLC is an investigational agent that has been obtained from Oncovir, Inc under a Clinical Trials Agreement between DFCI and Oncovir, Inc, dated May 2012. Under that agreement Oncovir, Inc will grant access to the Drug Master File for poly-ICLC for regulatory purposes and provides DFCI information necessary to pursue the clinical use of poly-ICLC. Poly-ICLC can be ordered directly from Oncovir, Inc, by submitting a purchase order to:

7.1.10 Accountability

The investigator, or a responsible party designated by the investigator, must maintain a careful record of the inventory and disposition of the agent (investigational or free of charge) using the NCI Drug Accountability Record or another comparable drug accountability form. (See the CTEP website at <http://ctep.cancer.gov/protocolDevelopment> for the “Policy and Guidelines for Accountability and Storage of Investigational Agents” or to obtain a copy of the drug accountability form.)

7.1.11 Destruction and Return

At the end of the study, unused supplies of poly-ICLC will be held by the IND holder for future use until they are out of date at which point they will be destroyed according to institutional policies. Destruction will be documented in the Drug Accountability Record Form.

CONFIDENTIAL

[figure not shown]
This document is confidential. Do not disclose or use except as authorized.

7.2 Personalized neoantigen peptides

7.2.1 Description

Personalized neoantigen peptides are comprised of up to 20 distinct peptides unique to each patient. Each peptide is a linear polymer of ~20 - ~30 L-amino acids joined by standard peptide bonds. The amino terminus is a primary amine (NH₂-) and the carboxy terminus is a carbonyl group (-COOH). Only the standard 20 amino acids commonly found in mammalian cells are utilized (alanine, arginine, asparagine, aspartic acid, cysteine, glutamine, glutamic acid, glycine, histidine, isoleucine, leucine, lysine, methionine, phenylalanine, proline, serine, threonine, tryptophan, tyrosine, valine). The molecular weight of each peptide varies based on its length and sequence and is calculated for each peptide.

7.2.2 Form

7.2.3 Storage and Stability

Personalized neoantigen peptides are stored frozen at -70 to -80°C. The thawed vials and the final mixture of personalized neoantigen peptides and poly-ICLC can be kept at room temperature but should be used within 6 hours after preparing the peptide + poly-ICLC mixture.

7.2.4 Compatibility

Personalized neoantigen peptides will be mixed with poly-ICLC just prior to use to prepare the final product (NeoVax).

7.2.5 Handling

There are no specific instructions for handling personalized neoantigen peptides.

7.2.6 Availability

The personalized neoantigen peptides are prepared by CSBio, Inc under contract with DFCI and will be supplied directly to the DFCI. It will be supplied from DFCI to other participating institutions.

CONFIDENTIAL

This document is confidential. Do not disclose or use except as authorized.

7.2.7 Preparation

The final step in the preparation of NeoVax (mixing with poly-ICLC) is conducted on the day of the scheduled vaccine administration as described in 5.2.1.1. Briefly, one vial each of the frozen personalized neoantigen peptides pools will be thawed the personalized neoantigen peptides will be combined and mixed with poly-ICLC within a properly certified biosafety cabinet.

7.2.8 Administration

Following mixing with personalized neoantigen peptides, the vaccine (peptide + poly-ICLC) will be administered as follows: using one syringe/needle per site 0.5 mL will be administered intradermally and 0.5 mL will be administered subcutaneously.

7.2.9 Ordering

The order for personalized neoantigen peptides to CSBio, Inc will be placed by the DFCI / Cell Manipulation Core Facility separately for each individual patient. Delivery time is anticipated to be 4 – 8 weeks.

7.2.10 Accountability

The investigator, or a responsible party designated by the investigator, must maintain a careful record of the inventory and disposition of the agent (investigational or free of charge) using the NCI Drug Accountability Record or another comparable drug accountability form. (See the CTEP website at <http://ctep.cancer.gov/protocolDevelopment> for the “Policy and Guidelines for Accountability and Storage of Investigational Agents” or to obtain a copy of the drug accountability form.)

7.2.11 Destruction and Return

Unused supplies of personalized neoantigen peptides will be released to the sponsor for further research or destroyed according to institutional policies. If unused personalized neoantigen peptides are destroyed this will be documented in the Drug Accountability Record Form.

8 CORRELATIVE/SPECIAL STUDIES

8.1 Pharmacodynamic Studies

The immunization strategy is a “prime-boost” approach, involving an initial series of closely spaced immunizations to induce an immune response followed by a period of

CONFIDENTIAL

This document is confidential. Do not disclose or use except as authorized.

rest to allow memory T-cells to be established. This will be followed by a booster immunization, and the T-cell response 4 weeks after this boost (16 weeks after the first vaccination) is expected to generate the strongest response and will be the primary immunological endpoint. Immune monitoring will be performed in a step-wise fashion as outlined below to characterize the intensity and quality of the elicited immune responses. Peripheral blood will be collected and PBMC will be frozen at two separate time points prior to the first vaccination (baseline) and at different time points thereafter as illustrated in Schema B and specified in the study calendar. Immune monitoring in a given patient will be performed after the entire set of samples from the induction phase and the maintenance phase, respectively, have been collected.

If sufficient tumor tissue is available, a portion of the tumor will be used to develop autologous melanoma cell lines for use in cytotoxic T-cell assays.

8.1.1 Screening *ex vivo* IFN- γ ELISPOT

For each patient, a set of screening peptides will be synthesized. The screening peptides will be 15-17 amino acids in length, overlapping by 11 amino acids and covering the entire length of each peptide or the entire length of the neoORF for neoORF-derived peptides. The entire set of patient-specific screening peptides will be pooled together at approximately equal concentration and a portion of each peptide will also be stored individually. Purity of the peptide pool will be ascertained by testing PBMC from 5 healthy donors with established low background in *ex vivo* IFN- γ ELISPOTs. Initially, PBMC obtained at baseline and at week 16 (the primary immunological endpoint) will be stimulated for 18 hours with the complete pool of overlapping 15-mer peptides (11 amino acids overlap) to examine the global response to the peptide vaccine. Subsequent assays may utilize PBMC collected at other time points as indicated.

If no response is identified at the primary immunological endpoint using the *ex vivo* IFN- γ ELISPOT assay, PBMC will be stimulated *in vitro* with the peptide pool for a longer time period (up to 10 days) and re-analyzed.

We are broadly interested in the immunogenic potential of the predicted neoantigens that have been used to formulate the study subject's personal vaccines. Given that patients will have completed vaccine dosing, subsequent profiling of the subject's immune responses necessarily will include analysis of antigen-specific immunity to the precise vaccine antigens that had been administered. The unused peptides are thus valuable reagents to enable these informative immune studies. For this reason, and under the request of the Overall PI, personalized neoantigen peptides may be transferred from the pharmacy department to the research lab.

8.1.2 Deconvolution of epitopes in follow-up *ex vivo* IFN- γ ELISPOT assays

Once an *ex vivo* IFN- γ ELISPOT response elicited by a overlapping peptide pool is observed (defined as at least 55 spot forming units / 10^6 PBMC or increased at least 3

CONFIDENTIAL

This document is confidential. Do not disclose or use except as authorized.

times over baseline), the particular immunogenic peptide eliciting this response will be identified by de-convoluting the peptide pool based into sub-pools based on the immunizing peptides and repeating the *ex vivo* IFN- γ ELISPOT assays.

For some responses, an attempt will be made to precisely characterize the stimulating epitope by utilizing overlapping 8-10 mer peptides derived from confirmed, stimulating peptides in IFN- γ ELISPOT assays

8.1.3 Additional assays conducted on a case-by case basis for appropriate samples

- The entire 15mer pool or sub-pools will be used as stimulating peptides for intracellular cytokine staining assays to identify and quantify antigen-specific CD4+, CD8+, central memory and effector memory populations
- Similarly, these pools will be used to evaluate the pattern of cytokines secreted by these cells to determine the T_H1 vs T_H2 phenotype
- Extracellular cytokine staining and flow cytometry of unstimulated cells will be used to quantify Treg and myeloid-derived suppressor cells (MDSC).
- If a melanoma cell line is successfully established from a responding patient and the activating epitope can be identified, T-cell cytotoxicity assays will be conducted using the mutant and corresponding wild type peptide
- PBMC from the primary immunological endpoint will be evaluated for “epitope spreading” by using known melanoma tumor associated antigens as stimulants and by using several additional identified mutated epitopes that were not selected to be among the immunogens
- Peptide ELISAs will be used to monitor humoral responses to the immunizing peptides

8.1.4 Immunohistochemistry

Immuno-histochemistry of tumor samples will be conducted to quantify CD4+, CD8+, MDSC, and Treg infiltrating populations.

CONFIDENTIAL

This document is confidential. Do not disclose or use except as authorized.

9 STUDY CALENDAR

	Initial Screening	Study Drug Preparation	Second Screening	Priming Phase							Boosting Phase							Long Term Evaluation	
Day ¹				1	4	8	15	22	29	50	78	85	106	134	141	162	190	Every 3 months ¹⁷	
Week				1	1	2	3	4	5	8	12	13	16	20	21	24	28	40-96	
Informed Consent	X																		
Medical History/Physical exam ²	X		X ¹⁹	X	X	X	X	X	X	X	X	X	X	X	X	X	X	X	
Staging scans ³	X									X						X		X ¹⁸	
Autoimmune panel ⁴	X																		
Pregnancy testing ⁵	X		X ¹⁹																
CBC w/diff, plts	X		X ¹⁹	X	X	X	X	X	X	X	X	X	X	X	X	X	X	X	
Serum Chemistry ⁶	X		X ¹⁹	X	X	X	X	X	X	X	X	X	X	X	X	X	X	X	
Infectious panel ⁷	X																		
Concomitant medications	X		X ¹⁹	X	X	X	X	X	X	X	X	X	X	X	X	X	X	X	
HLA class I and II testing ⁸	X																		
Blood draw for normal tissue sequencing ⁹	X																		
Melanoma resection ¹⁰		X																	
Pathology review		X																	
Vaccine preparation ¹¹		X																	
Leukapheresis ¹²			X												X				
Blood draw for immune response monitoring			X ¹³	X ¹³		X ¹⁴			X ¹⁵	X ¹⁵		X ¹⁶	X ¹⁵		X ¹⁵				
Vaccine administration				X	X	X	X	X	X	X	X		X		X				
Adverse event evaluation				X	X	X	X	X	X	X	X	X	X	X	X	X	X	X	

¹All study procedures should be performed within a +/- 3 day window unless specified otherwise.

²History and Physical examination include ECOG Performance Status and Vital Signs

³Initial screening scans (PET/CT or CT neck, chest, abdomen, and pelvis, and brain MRI for baseline assessment must be performed <4 weeks prior to surgery. Day 50 re-staging scans can be done between day 43 and 50; day 190 scans can be done between day 183 and day 190.

⁴ANA, anti-thyroglobulin antibodies, rheumatoid factor.

⁵Women of child-bearing potential must have a negative serum β -HCG pregnancy test during screening and within 7 days of starting treatment.

⁶Glucose, urea nitrogen, creatinine, sodium, potassium, calcium, total and direct bilirubin, AST, ALT, alkaline phosphatase

⁷ HBSAg, HBcAb, HCV, HTLV I/II, RPR, HIV 1 and 2 Ab test

⁸Molecular HLA typing to be performed by Tissue Typing laboratory

CONFIDENTIAL

This document is confidential. Do not disclose or use except as authorized.

⁹10 ml (one purple capped tube) of blood will be drawn and transmitted to the Broad Institute for whole exome sequencing.

¹⁰Resection of locoregional metastatic disease (regional lymph nodes, in transit metastases, satellite lesions, limited distant metastases) and primary tumor (if not yet removed) should occur within 3 weeks of study enrollment.

¹¹Vaccine preparation should begin immediately after the surgical specimen is deemed adequate for vaccine preparation and it has been determined that the primary melanoma and metastatic disease have been completely removed. Vaccine preparation should be completed within 8-10 weeks after this assessment.

¹²Patients will undergo leukapheresis procedure to collect sufficient amounts of PBMCs to allow comprehensive immune monitoring. The pre-treatment leukapheresis should be performed no sooner than 2 weeks after the surgery, prior to the first vaccine administration. A +/- 7 day window is allowed for the day 106 leukapheresis. If a patient is discontinued from active treatment (during Priming or Boosting Phase) and has not yet undergone the day 106 leukapheresis, the leukapheresis or a 50 ml blood draw should be performed no later than 14 days after the day of discontinuation.

¹³135 ml of blood should be drawn if pre-treatment leukapheresis cannot be performed. If pre treatment Leukapheresis was performed 20 ml should be drawn.

¹⁴If pre-treatment leukapheresis cannot be performed, there is no blood draw. If leukapheresis was performed, 60 ml of blood will be collected.

¹⁵200 ml

¹⁶200 ml of blood should be drawn if week-16 leukapheresis cannot be performed. If week -16 leukapheresis can be performed, there is no blood draw.

¹⁷ Follow-up: Every 3 months re-staging follow-up visits (+/- 1 week) should continue until initiation of a new therapy for recurrent disease, withdrawal of consent, or death whichever occurs first for a total of 2 years after treatment initiation.

¹⁸ Every 6 months

¹⁹ Assessments such as: Medical History / Physical Examination, lab tests and Con Meds can be done on Day 1 visit (previous starting treatment) if needed

CONFIDENTIAL

This document is confidential. Do not disclose or use except as authorized.

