1.3 Secondary Objectives

- 1.3.1** To assess the induction of specific cellular immune responses following administration of NeoVax
- 1.3.2** To determine the proportion of patients alive without progression at two years after surgery following administration of NeoVax

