4 REGISTRATION PROCEDURES

Eligibility will be confirmed and participants registered on 2 separate, serial occasions on this trial:

- 1. Prior to surgical resection:**
Prior to initial surgical resection, the patient is screened for eligibility using the initial eligibility checklist. Once overall trial initial eligibility is confirmed, patient is registered, undergoes surgical resection and preparation of the participant's vaccine is initiated.
- 2. Prior to first vaccination:**
As participant's 1st study vaccine dose may not be administered until 10-17 weeks from initial study registration, there will be a secondary "screen" conducted prior to first vaccination to ensure s/he meets criteria to receive study treatment.
If confirmed eligible for this next phase of the study (eligible to treat as per sections 3.1.2 and 3.2), participant will proceed to receive vaccines on study.

CONFIDENTIAL

This document is confidential. Do not disclose or use except as authorized.

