5.8 Duration of Follow Up

Patients removed from study for unacceptable adverse events will be followed until resolution or stabilization of the adverse event.

Every 3 months (“close observation”) follow-up visits should continue until initiation of a new therapy for recurrent disease or withdrawal of consent, whichever occurs first, for a maximum of 2 years after the surgery. Patients will undergo disease restaging scans every 6 months for 2 years after the surgery.

CONFIDENTIAL

This document is confidential. Do not disclose or use except as authorized.

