10 MEASUREMENT OF EFFECT

10.1 Antitumor Effect– Solid Tumors

For the purposes of this study, patients should be re-evaluated for disease recurrence every 12 weeks.

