14.2 Analysis of Secondary Endpoints

Secondary endpoints in this clinical trial will: (a) assess the induction of IFN- γ T-cell response to the total peptide pool, and (b) estimate the proportion of patients alive without disease progression at two years after resection. Analyses of these secondary endpoints will be based on the 15 patients treated at the recommended vaccine dose.

The induction of IFN- γ T-cell response will be based on ELISPOT assessments taken prior to vaccine administration and at week 16. The proportion of patients who achieve more than 55 SFU/ 10^6 PBMC *or* 3 times their baseline level will be presented with a 90% exact binomial confidence interval. Based on a cohort of size 15, the confidence interval will be no wider than 0.46.

The proportion of patients alive, without disease progression at two years after resection will be estimated using the method of Kaplan-Meier. The endpoint will be calculated as the time between pathological confirmation of complete resection and the first of disease recurrence or death. Patients who are disease-free at the time of study reporting will have their follow-up censored at the time of the last study visit. Patients who were disease-free at the time of their last assessment and who have either been lost to follow-up or withdrawn consent will have their follow-up censored at the time of the last study assessment. The proportion of patients alive and disease-free at two years will be presented with 90% confidence intervals estimated using log(-log(DFS)) methodology.

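### Section 5.8 and the study calendar put restaging scans on different clocks, so a site following the calendar need not scan at the two-year-after-surgery landmark

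*Combined protocol and SAP*

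**What the plan says.** **Endpoint.** Objective 1.3.2 reads: "To determine the proportion of patients alive without progression at two years after surgery following administration of NeoVax". Section 14.2 starts the clock within days of surgery: "The endpoint will be calculated as the time between pathological confirmation of complete resection and the first of disease recurrence or death".

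**Scans.** Three places set the schedule.
- Section 5.8: "Patients will undergo disease restaging scans every 6 months for 2 years after the surgery". The three-monthly visits in the same section run "for a maximum of 2 years after the surgery".
- Section 9, the calendar, numbers its days from first vaccination. Footnote 3 says: "Day 50 re-staging scans can be done between day 43 and 50; day 190 scans can be done between day 183 and day 190". Footnote 18 sets later scans at six-month intervals without saying from which date. The long-term column covers weeks 40 to 96, and footnote 17 ends follow-up two years after treatment initiation.
- Section 10.1: "patients should be re-evaluated for disease recurrence every 12 weeks". It does not say whether by imaging or by examination.

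**Lag between the clocks.** Section 4 says that the first dose "may not be administered until 10-17 weeks from initial study registration". Calendar footnote 10 puts surgery within 3 weeks of enrolment.

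**Recurrence and censoring.** Section 10.1.1 accepts an unequivocal new lesion on examination or imaging. An equivocal lesion that is later confirmed is dated to the scan that first showed it. Section 14.2 says: "Patients who are disease-free at the time of study reporting will have their follow-up censored at the time of the last study visit". For patients lost or withdrawn, it uses the last study assessment instead.

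**The concern.** A two-year DFS proportion is only as good as the disease assessment near two years. Section 5.8 places a scan at that point. The calendar does not, because its scans are counted from a date 7 to 17 weeks later than the endpoint's origin and the six-month step has no stated anchor.

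A recurrence that only imaging can show, arising between the last calendar scan and the landmark, is either not found or is found at a later scan and dated after two years. Either way the patient counts as disease-free at two years, and the error runs in the vaccine's favour.

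Settling the follow-up end date alone does not solve this. If follow-up ends two years after surgery, a fourth scan counted from day 190 is never done. If it ends two years after treatment initiation, that scan may be done, but after the landmark.

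**Working it through.** The documents state no gap between last scan and landmark and no precision figure for DFS, so there is no plan figure to reproduce. The check is date arithmetic followed by a bound on the bias.

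**Inputs from the documents:** registration to first vaccination 10-17 weeks (section 4); registration to surgery 0-3 weeks (footnote 10); scan at day 190, then every 6 months (footnotes 3 and 18); landmark 2 years after surgery, taken as 104 weeks (1.3.2); two-year recurrence of 60-80% for resectable stage IIIB/IIIC (section 2.2); 15 patients (14.2).

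**Step 1, lag from surgery to first vaccination.** Shortest 10 − 3 = 7 weeks; longest 17 − 0 = 17 weeks.

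**Step 2, later scans counted from day 190.** Day 190 is 189/7 = 27 weeks after day 1. Steps of 26 weeks give weeks 27, 53, 79 and 105 after first vaccination. Adding the lag:

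| Scan | Weeks after surgery |
|---|---|
| 1 | 34-44 |
| 2 | 60-70 |
| 3 | 86-96 |
| 4 | 112-122 |

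The last scan before week 104 is the third, so the gap is 104 − 96 = 8 to 104 − 86 = 18 weeks. The fourth is beyond the calendar's week 96 and beyond the end in 5.8. It lies one week past footnote 17's end (105 against 104 weeks), within that footnote's 1-week window, and falls 8 to 18 weeks after the landmark.

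**Step 3, other readings.**
- First long-term scan at week 40, then 66 and 92. For lags of 7 to 12 weeks the last scan is at 92 + lag = 99 to 104, a gap of 5 to 0 weeks. From a lag of 13 weeks the week-92 scan falls after the landmark, so the last one before it is at 66 + lag = 79 to 83, a gap of 25 to 21 weeks.
- Section 5.8: scans at 6, 12, 18 and 24 months after surgery, a nominal gap of 0.

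**Step 4, bound on the bias.** Assume a constant hazard h = −ln(1 − R)/104, where R is the two-year recurrence risk, and no detection after the last scan. The overstatement is S(last scan) − S(104), with S(t) = exp(−ht).

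| R | S(104) | S(96) | Difference | S(86) | Difference |
|---|---|---|---|---|---|
| 60% | 0.400 | 0.429 | 0.029 | 0.469 | 0.069 |
| 80% | 0.200 | 0.226 | 0.026 | 0.264 | 0.064 |

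On the day-190 reading this is 2.6 to 6.9 percentage points, or 15 × 0.026 = 0.4 to 15 × 0.069 = 1.0 patients. On the week-40 reading the same formula gives 0 to about 2 points for lags up to 12 weeks. For lags of 13 to 17 weeks it gives about 8 to 10 points (S(83) − S(104) = 0.077 to 0.081; S(79) − S(104) = 0.094 to 0.099).

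**Step 5, scale.** At DFS 40% with 15 patients and no earlier censoring, the standard error on the log(−log) scale is √(0.6/(0.4 × 15))/|ln 0.4| = 0.345. The 90% interval is then about 20% to 60%.

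**Step 6, what examinations cover.** Visits every 12 or 13 weeks from week 28 up to week 96 leave about 1 to 12 weeks between the last examination and the landmark at the lags checked. The bound in step 4 gives no credit for these.

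**The case against.** The strongest reply is that section 5.8 already does the right thing. It counts scans from surgery and puts one at 24 months, and nothing in the documents ranks the calendar above it. That stands. A reader might infer that the trial's last scheduled scan simply is 8 to 18 weeks before the landmark. The documents do not support this: it is one reading of an unanchored footnote, and 5.8 contradicts it.

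Second, recurrence does not depend on scans alone. Physical examination continues every three months, 10.1 asks for re-evaluation every 12 weeks, and 10.1.1 accepts a finding on examination. That also stands. It would be too strong to say that patients are credited as disease-free unchecked after the last scan; only recurrences visible on imaging alone are at issue.

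Third, a reader might blame the censoring rule in 14.2. Moving the censoring date back to the last scan would not recover missed recurrences, because the Kaplan-Meier curve would stay flat from there to week 104. If later clinical recurrences were still counted, the smaller risk set would add a bias of its own. Since 10.1.1 accepts examination, a visit with an examination is arguably already a disease assessment. What is left is that 14.2 uses two different terms for disease-free patients.

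Fourth, the effect is small, and no test or decision rule uses this endpoint. True, although a confidence interval expresses sampling error, not a bias in one direction.

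None of this removes the conflict between 5.8 and the calendar.

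**Conclusion.** The point holds as an internal contradiction with a modest consequence. Section 5.8 places scans on the endpoint's clock. Calendar footnotes 3, 17 and 18 do not, and 10.1 adds a third interval. No reading of the calendar guarantees a scan at two years after surgery across the whole 7 to 17 week lag; 5.8 does.

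If the calendar is followed with scans counted from day 190, two-year DFS is biased upward by at most about 3 to 7 percentage points, or up to 1 of 15 patients. This bound assumes a constant hazard, 60-80% two-year recurrence and no clinical detection in the gap, so the real figure should be lower on that reading. Counting from week 40 instead moves the bound to between 0 and about 10 points, depending on the lag. Against an interval of about 20% to 60%, and for a descriptive secondary endpoint, this is worth correcting but does not threaten the trial's primary conclusions.

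**What to change.** Reconcile 5.8, 10.1 and calendar footnotes 3, 17 and 18 to a single scan clock that matches the endpoint's origin, so that a scan falls at 24 months after surgery as 5.8 already provides. State the anchor date in footnote 18, use the same follow-up end in 5.8 and footnote 17, and say in 10.1 whether the 12-week re-evaluation means examination, imaging or either.

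In 14.2, use one censoring term for all disease-free patients: the last disease assessment, by examination or imaging as 10.1.1 allows. This is for consistency and does not remove the bias on its own.

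The cost is amendment wording plus at most one scan per patient beyond what the calendar yields. Section 5.8 already calls for that scan.
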